Patients who have a COVID-19 positive test and are subsequently enrolled without any intermediate hospital activity will be considered 'treated' for the purpose of all hospital outcome analyses which occur within 28 days of the date of their first COVID-19 positive test. If a patient attends A&E after enrolment but before they received a pulse oximeter, they will still be considered as having received the intervention. This is because the evaluation seeks to understand the usefulness of CO@h as it is used in practice.

However, A&E departments are also one of the services that can refer patients to CO@h. In this case, the A&E attendance by definition pre-dates onboarding (as the pulse oximeter was dispensed following A&E attendance). Here, it is not appropriate to count the patient as having had the intervention when analysing A&E attendances. However, it is also not appropriate to exclude these patients from the analysis for outcomes that occur before onboarding, as this would introduce bias compared with patients not enrolled in CO@h. We can identify the cases described above by triangulating the date of onboarding with any dates of A&E, thereby determining whether patients were (most likely) enrolled through A&E. Using these data, we can set the intervention receipt (which is used in the fuzzy part of the design) to 1 (enrolled) or 0 (not enrolled) depending on the outcome – ie for a patient enrolled following an A&E attendance, this attendance would still count towards the outcome in the model for A&E attendances, but treatment receipt (enrolled) would be set to 0. However, for the emergency admission outcome, the same patient's subsequent emergency admission (if one occurred) would have enrolment set to 1.

Sensitivity analyses

We will undertake a range of sensitivity analyses to identify whether the resulting treatment effect estimates are reliable. These will be carried out on each of the primary outcomes (critical care bed use, total bed days in critical care, and death) but only on the secondary outcomes if these show statistically significant treatment effects. Unless otherwise stated, the design choices used in the main analysis (eg fuzzy design, window, order of polynomial, etc) will be the same as in the main analysis. The sensitivity analyses will include:

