1. Intention-to-treat analysis – we will use a sharp design (without taking account of compliance/oximeter receipt) to estimate the average effect of intervention eligibility at age 65, ie an intention-to-treat analysis.
2. Placebo outcomes – we will undertake statistical tests for treatment effects for each of the baseline variables and plot the means for each group, weekly averages and fitted constants to identify any evidence of infringement of the assumption of comparability of the groups.
3. Test of treatment assignment – we will use a binomial test to check that, within the specified window, treatment can be considered randomly assigned.
4. Influence of window choice – we will test a selection of windows smaller than the one used in the main analysis (minimum 10 patients either side of the threshold). We will not use larger windows as this may lead to biased estimates due to imbalances in baseline variables.¹⁷ By using smaller windows, this problem is avoided while also identifying whether restriction of the cohort to those increasingly closer to the threshold affects the treatment effect estimates. We will plot the resulting point estimates and confidence intervals.
5. Placebo thresholds – we will estimate treatment effects at both a lower and a higher threshold than age 65 to check that these spurious, placebo thresholds result in a treatment effect of zero. For these checks, we will only use control and treated patients,

respectively.¹⁷ We will test at thresholds centred on the first mass point past the end boundaries of the window used in the main analysis. We will use the same window size (ie number of mass points either side) as in the main analysis.¹⁷

6. Placebo study period – we will use data for a period before CO@h was implemented (ie in CCGs before they implemented CO@h) to check that there is no discontinuity in outcomes in a window around age 65 when no treatment was available. This will be a sharp RDD (as there will, by definition, be no intervention available). This sensitivity analysis will only be conducted if the intention-to-treat analysis using a sharp RDD (sensitivity analysis #1) is statistically significant.
7. Sensitivity to unmeasured confounding – we will calculate Rosenbaum’s sensitivity bounds, within the context of a local randomisation RDD, to estimate how large an unobserved confounder would need to be to affect the conclusions of the study.^{19,27}

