We are only including data from patients from CCGs from the period at which they have reported that CO@h is fully operational. By excluding data from areas that have not, or have not yet, implemented CO@h, or where they are just ramping up the service, we want to evaluate the intervention once implemented, while also ensuring the best chance of finding a discontinuity in treatment by age in order to be able to use an RDD. It may be that these 'adopters' are different from 'non-adopters' or 'late adopters', and that the effect may be different when the intervention has had time to embed (new pathways established, new ways of working etc), or after the eligibility criteria have changed, which may affect the generalisability of our results. However, as the comparison group is from within the same areas, this does not affect the internal validity or invalidate the RDD.

Due to severe pressures within the NHS, collection of onboarding data in many areas has been delayed or diminished. Unless these data are retrospectively and – at least in some areas comprehensively – collected within the time frame of this evaluation, this study could be seriously undermined. Although a sharp design is still possible, in that we can evaluate the effect of being 'eligible' for enrolment (ie in effect treating all patients aged 65 or over as having the intervention and all under 65 years of age as not) in those CCGs that are expected to have had higher levels on onboarding, this would understate the treatment effect, as treatment group non-compliers (patients not receiving oximeters when they should have) would not be accounted for using the 'fuzzy' approach.

By limiting the analysis to patients with a COVID-19 positive test in those areas that were fully operational, that abided by the original CO@h criteria and provided onboarding data before the change in age criteria was introduced, we may find that our sample size and in particular the number of patients with primary outcomes may be very small. As a result, the study may be underpowered.

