As the PRINCIPLE trial also used an age threshold of age 65 for trial inclusion, there is a risk that this will introduce bias in our analysis. We will limit the risk of the PRINCIPLE trial biasing our results by checking the number of patients enrolled in the trial by area and age band and end the study period of our evaluation before a maximum of 5% of patients around the threshold have been enrolled in the PRINCIPLE trial.

This analysis builds on the assumption that there are no other differences in care of patients above and below 65 years of age that would affect the hospital outcomes of COVID-19 positive patients. We do not know of any such interventions but, if they exist, they may bias our results. We may be able to indirectly examine this to a certain extent by checking that there is no discontinuity in outcomes at age 65 in a period before the CCGs implemented CO@h (ie the 'placebo outcomes' sensitivity analysis).

There is a substantial risk to the execution and validity of the study if we cannot access onboarding data. Currently onboarding data is potentially going to be delayed, especially from CCGs that have been badly hit by the third pandemic wave, and/or may be incomplete. These data are necessary to allow us to estimate the effect of being enrolled in CO@h. In its absence, we can run an intention-to-treat analysis, estimating the effect of treatment eligibility, ie treat all non-CEV patients aged 65 or above as receiving CO@h and all non-CEV patients below as not receiving the intervention (a 'sharp' design). However, it is possible that compliance will not be high; therefore, this analysis is less likely to find an effect even if onboarding did affect outcomes, due to the added noise of non-compliers. It may however still provide a useful indication in the absence of onboarding data: a significant intervention effect would indicate that CO@h affected patients' outcomes (subject to sensitivity analyses), while a lack of a statistically significant effect would be non-informative as it would not be possible to unpick whether this is due to low uptake of the CO@h programme, the 65+ threshold not being complied with, or the CO@h programme not having the anticipated effect on outcomes.

If interim analyses are performed before receipt of final data, only the final analyses may be published.

Acknowledgements

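### The pre-CO@h placebo check looks only for the absence of a jump at 65 and never sets that jump against the CO@h-period jump, so an imprecise null could be read as support

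*SAP*

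**What the plan says.** SAP, Sensitivity analyses, item 6 (Placebo study period) applies a sharp RDD to CCG data that pre-date the programme. The stated purpose is "to check that there is no discontinuity in outcomes in a window around age 65 when no treatment was available". It is conditional: "This sensitivity analysis will only be conducted if the intention-to-treat analysis using a sharp RDD (sensitivity analysis #1) is statistically significant".

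The item gives no dates for the placebo period, no expected number of patients, no jump small enough to ignore, and no comparison with the estimate from item 1 (the sharp ITT analysis).

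Strengths and limitations says what the check is for. It states: "This analysis builds on the assumption that there are no other differences in care of patients above and below 65 years of age" (differences, that is, with a bearing on outcomes). About the pre-implementation data it then adds: "We may be able to indirectly examine this to a certain extent by checking that there is no discontinuity in outcomes at age 65". The same section warns, about the main analysis, that "the study may be underpowered".

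**The concern.** Item 6 runs only after the sharp ITT analysis is significant. At that point the question is whether something other than CO@h that changes at 65 could account for the jump just found. That calls for comparing two jumps. Item 6 looks at one of them, against zero. A significant jump in one period and a non-significant jump in the other is not evidence that the jumps differ.

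Zero is also not a safe benchmark. The Background section says that PRINCIPLE has enrolled since 17 April 2020, and the section on study period says its criteria imply the same discontinuity at 65 as CO@h. A placebo period after that date may already contain an age-65 intervention that the SAP itself names.

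At stake is how a positive finding is interpreted. If an imprecise null is reported as a clean check, an effect that belongs to something else at 65 could be credited to CO@h.

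**Working it through.** **Inputs from the SAP** (Power calculation, Table 1 and its note): two-sided 5% test, 80% power, equal groups, full compliance, and the 2.0% versus 1.5% cell with total N = 21,590. **Assumption:** the SAP gives no placebo N, so the ratio r = N(placebo)/N(main) is varied.

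**1. The plan's own figure.** Per group, n = [1.960·√(2·0.0175·0.9825) + 0.8416·√(0.02·0.98 + 0.015·0.985)]² / 0.005² = (0.3635 + 0.1560)² / 0.000025 ≈ 10,795. The total is 21,590, which matches. All 21 cells of Table 1 reproduce by this formula.

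**2. Chance that the placebo test misses a jump that explains the whole effect.** Suppose the same non-CO@h jump is present in both periods. Let z be its expected test statistic in the main sample. In the placebo sample this becomes d = z·√r, and the miss rate is 1 − P(|Z + d| > 1.96). Each patient has only one first positive test, so the two periods contain different patients. For a given true jump, the requirement that item 1 be significant does not change the miss rate.

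- Case A: the main sample has 80% power for the jump, so z = 1.96 + 0.84 = 2.80.
- Case B: the jump just reaches p = 0.05 in the main sample, so z = 1.96.

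| r | d, case A | Missed, case A | d, case B | Missed, case B |
|---|---|---|---|---|
| 2 | 3.96 | 2% | 2.77 | 21% |
| 1 | 2.80 | 20% | 1.96 | 50% |
| 0.5 | 1.98 | 49% | 1.39 | 72% |
| 0.25 | 1.40 | 71% | 0.98 | 83% |

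Direct two-proportion power for 2.0% versus 1.5% agrees with case A: 80%, 51% and 29% at r = 1, 0.5 and 0.25.

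**3. A jump that explains half the effect** (2.0% versus 1.75%) is detected with 27% power at r = 1 and 16% at r = 0.5.

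**4. Precision.** With a 2% risk in both groups, the 95% CI half-width is 1.96·√(2·0.02·0.98/n). At r = 1 (n = 10,795) it is 0.37 points. At r = 0.5 (n ≈ 5,398) it is 0.53 points, wider than the 0.50-point effect. If the true placebo jump is zero, placing the whole 95% CI within ±0.5 points with 80% probability needs N = 2·[2·0.02·0.98·(1.960 + 1.282)²/0.005²] ≈ 32,950, about 1.5 times 21,590.

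**5. Precision of the contrast.** The SE of the difference between the two jumps, relative to the SE of the main jump, is √(1 + 1/r): √2 = 1.41 at r = 1 and √3 = 1.73 at r = 0.5.

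**The case against.** A reader might infer that the SAP will treat a non-significant placebo result as proof that nothing else changes at 65. The document does not say so. The limitations section says only that the assumption may be examined indirectly and to a certain extent, and it concedes that unknown age-65 interventions could bias the results. Elsewhere in that section the authors call a null sharp analysis without onboarding data non-informative, so they know that absence of significance is not absence of effect.

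Nor is item 6 clearly a bare p-value check. The introduction to the sensitivity analyses says: "Unless otherwise stated, the design choices used in the main analysis (eg fuzzy design, window, order of polynomial, etc) will be the same". The main analysis includes a confidence interval and the power of the Neyman test, and both plausibly carry over.

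A reader might also infer that the placebo sample must be smaller. That is conjecture. The placebo analysis needs no onboarding data, whereas the main sample is cut by onboarding availability and by several possible end dates. A late-starting CCG could contribute a longer period before CO@h than after it.

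Finally, this is one of seven sensitivity analyses. Rosenbaum bounds (item 7) address unmeasured confounding in general, and PRINCIPLE has its own 5% enrolment limit.

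These points limit the claim but do not remove it. A hedge is not a reading rule. Item 4 promises point estimates and intervals expressly, while item 6 does not, and nothing says how an interval would be used or when the check is inconclusive. The argument does not need a smaller placebo sample: at equal size the miss rate is already 20% to 50%. Rosenbaum bounds do not tell the reader how to interpret item 6.

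**Conclusion.** The point holds in a limited form. Item 6 asks only whether a jump is absent before CO@h and makes no comparison with the CO@h-period jump, so an imprecise null could be taken as support for the assumption of no other difference in care at 65.

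A non-CO@h jump large enough to explain the whole effect would go undetected 20% to 50% of the time at equal N, 49% to 72% at half and 71% to 83% at a quarter. With twice the N the range falls to 2% to 21%. These figures assume an identical jump in both periods, normal approximations and a two-sided 5% reading of the check. They do not show that such a jump exists or is likely. The documents do not support saying that the authors will misread the result, or that the placebo sample will be smaller. The matter concerns the wording of a sensitivity analysis and leaves the main estimate untouched.

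**What to change.** In item 6:

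- State the placebo dates, and use the same CCGs and the same age window as the sharp ITT analysis.
- For each primary outcome, report the placebo-period jump with its 95% CI beside the sharp ITT jump.
- Add the difference between the two jumps (CO@h period minus pre-CO@h period) with a 95% CI.
- Say that the check is inconclusive if the placebo CI does not exclude a jump as large as the ITT estimate.
- State that the difference assumes any non-CO@h jump is constant across the two periods. Changes in the epidemic or in PRINCIPLE enrolment could break this, which is a reason to keep the difference as a sensitivity analysis.

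In Strengths and limitations, correct the cross-reference: the pre-implementation check is called 'placebo outcomes' there, but that is item 2 (tests on baseline variables). The check meant is item 6.

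The cost is a few lines of text and one contrast on data already planned. The differenced estimate is less precise (SE ×1.41 at equal N, ×1.73 at half). For example, if the whole effect is due to CO@h and the main sample has 80% power, the contrast at equal N has z = 2.80/1.41 = 1.98, or about 51% power. Its interval should therefore be read as a range and not as a second test that the main result must pass.

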At the time of writing, it is unclear what volume of patients have been referred to the CO@h pathway, and what onboarding data will be available due to pressure on the system to cope with the pandemic. As a result, the study may be underpowered. This risk is further exacerbated by the fact that the primary outcomes relate to use of critical care beds and mortality. The mixed-methods study of pilots of remote home monitoring models in England

found that for the pre-hospital model of CO@h, although 10% (174/1,737) of patients that were monitored deteriorated and were escalated, 0.2% (3/1,737) of patients were admitted to ICU and 1% (20/1,737) died.¹ See the Power calculation section for further details

All decisions taken after this statistical analysis protocol (SAP) has been finalised will be documented and justified in an addendum to it. We may run interim analyses on incomplete data to provide the CO@h programme team with some preliminary indications of results. The results of the final analysis will be published in line with the Health Foundation's Improvement Analytic Unit's (IAU's) aim of openness and transparency.

Study outcomes

We will analyse outcomes in the 28-day period following a COVID-19 positive test (ie equal to or less than 28 days from a positive test, with the date of the first COVID-positive test being equal to day zero). We are limiting most of the outcomes to binary variables (ie capturing whether there was an A&E attendance rather than the number of attendances); this is because of the short follow-up period and likely sparsity in hospital event counts other than 0 and 1 (which we will confirm on receipt of the data). The following outcomes will be included:

- Type 1 A&E attendance (binary outcome yes/no)
- Emergency admission (binary outcome yes/no)
- Critical care bed use (binary outcome yes/no)
 - This will capture a stay in ICU at any point during an admission, which could be as a result of either an emergency or an elective admission.
 - This variable includes level 2 and level 3 beds, as well as beds under code 5 (flexible critical care beds where there is a mix of level 2 and level 3 beds) and code 90 (temporary use of non-critical care beds).¹²
- Total emergency hospital bed days

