For the procedure in (a), Cattaneo et al recommend that the p-value chosen for these tests is at least 0.10 and preferably 0.15.¹⁷ As we have a large number of baseline characteristics, a p-value of 0.10 should provide a reasonably conservative threshold, given that the chances of identifying a significant difference in at least one variable increase with the number of variables tested.²³ The results of these tests will be tabulated and plotted, showing how the minimum p-value changed against each window length from a window length of 1 week either side, up until the resulting minimum p-value remains consistently below 0.05.

Although the window selection can be done directly through the 'rdrandinf' command (within the 'rdlocrand' R package), we will calculate it using the separate window selection function 'rdwinselect', so that the window selection process is completed independently of the main analysis.²⁴

Baseline variables

The baseline variables that we will check and use to identify the age window for analysis are:

- Gender
- Ethnicity
- IMD quintile
- IMD health deprivation and disability quintile
- Smoker (yes/no)
- Obesity (yes/no)
- Diabetes (yes/no)
- Multimorbidity (yes/no), ie whether a patient had two or more long-term conditions. We will use the list of conditions in the Cambridge Multimorbidity Score,²⁵ based on a list of conditions recorded in GP records and available in GDPPR and also used in Stafford et al²⁶.
- Region – as a proxy for other unobservable characteristics, as regions may have differing rates of COVID-19 and therefore also hospital pressures, which may affect patients' outcomes.

* Using power = 80%, alpha = 5%, and two-sided test.

Main analysis

In the main analysis, we will estimate a treatment effect based on the difference in means between the treated and untreated. Using randomisation inference, 10,000 simulated draws based on Fisher's exact approach to null-hypothesis testing will be used to estimate p-values of zero effect. We do not expect to have to transform the outcomes – as we do not expect the outcomes to vary with age within the chosen window – therefore we will use a polynomial of order zero (ie a constant within-group average outcome, which is the standard in the local randomisation approach. The plots created in the prior descriptive analysis will be used to confirm this).

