(White, Black, Asian, Mixed and Other). Depending on the achieved power, this may be limited to a broader group of ethnicities (eg 'ethnicities other than White'). Once we know more about the quality of onboarding data and numbers of patients enrolled, we will make an assessment as to what is possible in terms of subgroup analyses.

Reporting

Our reporting of the study will aim to meet the requirements of the STROBE checklist for the reporting of cohort studies.³⁰

Power calculation

A set of power calculations for binary outcomes (eg ICU: yes/no) are shown in Table 1, below.

Table 1: Total sample sizes resulting from power calculations

| Total sample sizes (N) | | Relative risk in treated group | | |
|---------------------------|-------|--------------------------------|--------|---------|
| | | 50% | 75% | 90% |
| Baseline risk | 10.0% | 870 | 4,010 | 26,990 |
| | 5.0% | 1,812 | 8,404 | 56,816 |
| | 4.0% | 2,282 | 10,602 | 71,730 |
| | 3.0% | 3,068 | 14,266 | 96,584 |
| | 2.0% | 4,638 | 21,590 | 146,294 |
| | 1.0% | 9,346 | 43,568 | 295,422 |
| | 0.5% | 18,766 | 87,522 | 593,680 |

Note: equal sized treatment and control groups of N/2; full compliance assumed, two-sided tests; power 80%; alpha 5%.

The power calculations are based on standard large sample approximations. Power calculations using Fisher-based randomisation inference produce similar results to those based on large sample approximations. For example, assuming two equally sized groups, a two-sided test at the 5% significance level, and an outcome of 2% in the control group and 1.5% in the treated group, a sample size of around 22,000 (11,000 in each group) would be required to achieve a power of 80% (based on a simulation with 10,000 draws).

These power calculations demonstrate that relatively large samples will be required to identify treatment effects of CO@h on the primary outcomes, particularly for infrequent outcomes such as ICU admittance. For reference, the mixed-methods study of pilots of remote home monitoring models in England found that for the pre-hospital model of CO@h, approximately 8% of onboarded patients attended A&E, 5% were admitted to hospital in an emergency, 0.2% were admitted to ICU and 1% died.¹

Strengths and limitations

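### The pre-CO@h placebo-period check is run only after a significant intention-to-treat result, so it cannot help explain a null caused by an opposing difference at exactly age 65

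*SAP*

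**What the plan says.** The introduction to the SAP's Sensitivity analyses section says the analyses will be done for each primary outcome (critical care bed use, critical care bed days, death). Only for secondary outcomes does it make them depend on significance. Item 6, the placebo study period, applies a sharp RDD at age 65 to data from CCGs before they introduced CO@h. It carries its own condition: "This sensitivity analysis will only be conducted if the intention-to-treat analysis using a sharp RDD (sensitivity analysis #1) is statistically significant". No reason is given, and no other numbered sensitivity analysis has such a condition for the primary outcomes.

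Strengths and limitations states that the design assumes no other difference in care above and below 65 that would affect outcomes. On testing that assumption it says: "We may be able to indirectly examine this to a certain extent by checking that there is no discontinuity in outcomes at age 65". The data meant are those that predate CO@h, as in item 6, but the condition is not mentioned there. The check is also labelled the placebo outcomes analysis, which is item 2 (tests on the baseline variables), not item 6.

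**The concern.** The SAP names one way to test empirically whether something other than CO@h changes at 65, and then makes it depend on the main sharp result. If that result is significant, the placebo period can show whether a discontinuity was already there. If it is not, the check is dropped. A non-significant result is what one would see if CO@h reduced events and another difference at 65 raised them by a similar amount. The protection therefore works in one direction only.

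At stake is the reading of a null result. Without the placebo period, the report cannot distinguish a programme with little effect from a benefit offset by something else at 65, even though the pre-CO@h data are already planned for. The decision to run a validity check would also be taken after seeing the result it is meant to test.

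**Working it through.** **1. Could another planned check replace item 6?** Take a difference in outcomes or care located exactly at 65.

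- Placebo thresholds (item 5) are centred just past the ends of the main window, away from 65.
- Smaller windows (item 4) still straddle 65, so the jump stays in every estimate.
- Outcome plots by week of age (Basic descriptive analysis and diagnostic checks) show only the net discontinuity, CO@h and rival together.
- Item 2 tests baseline variables, not outcomes. Item 3 and the density check concern numbers of patients.
- Rosenbaum bounds (item 7) say how large a confounder would have to be, not whether one exists.

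Only item 6 looks at outcomes at 65 without CO@h.

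**2. Reproducing the plan's own figure.** Power calculation assumes "equal sized treatment and control groups of N/2; full compliance assumed", two-sided 5% tests and 80% power. Its worked example has "an outcome of 2% in the control group and 1.5% in the treated group". With p1 = 0.020, p2 = 0.015 and pbar = 0.0175:

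n per group = [1.960·√(2·pbar·(1−pbar)) + 0.842·√(p1(1−p1) + p2(1−p2))]² / (p1−p2)² = 10,795

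The total is 21,590, which is the Table 1 entry. All 21 cells of Table 1 reproduce with this formula, without continuity correction.

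**3. How often would the check be skipped?** From the SAP: n = 10,795 per group, 2% control risk, true relative risk 0.75, full compliance. Assumed, because the SAP gives no value: an adverse jump at 65 of ratio J unrelated to CO@h, and a placebo-period sample of the same size.

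Let d = p2 − p1, se0 = √(2·pbar·(1−pbar)/n) and se1 = √((p1(1−p1) + p2(1−p2))/n). Then

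P(significant) = Φ((−1.96·se0 − d)/se1) + 1 − Φ((1.96·se0 − d)/se1)

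- CO@h period: p1 = 0.02, p2 = 0.02 × 0.75 × J.
- Placebo period: p1 = 0.02, p2 = 0.02 × J.

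For J = 1.20 in the CO@h period, p2 = 0.018, d = −0.002 and se0 ≈ se1 ≈ 0.001858. The two tails are 0.188 and 0.001, together 0.19.

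| J | Eligible risk, CO@h period | ITT significant | Check skipped | Eligible risk, placebo period | Power of check if run |
|---|---|---|---|---|---|
| 1.10 | 1.65% | 48% | 52% | 2.20% | 18% |
| 1.20 | 1.80% | 19% | 81% | 2.40% | 52% |
| 1.33 (exactly 1/0.75) | 2.00% | 5% | 95% | 2.67% | 90% |

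**4. The condition can fail without any bias.** If eligibility raises receipt by only a share r, the eligible risk is 0.02 × (1 − 0.25·r). Values of r are assumed.

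- r = 1: 1.50%, ITT significant 80% of the time.
- r = 0.5: 1.75%, 27%.
- r = 0.3: 1.85%, 13%.

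Study design and Strengths and limitations both expect non-compliers, so a non-significant sharp result is likely and item 6 would probably not be run.

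**5. Sensitivity to the placebo sample size.** With 2,000 per group in the placebo period instead of 10,795, the same formula gives power of about 14% for J = 1.20 and 29% for J = 1.33.

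**The case against.** A reader might go further and infer that a benefit masked by rising risk with age would never be detected. The eligible group is always the older one, and the main model fits no age slope because, in the SAP's words, "as we do not expect the outcomes to vary with age within the chosen window". The document does not support that reading. Three checks that address a smooth gradient run on the primary outcomes whatever the intention-to-treat result: outcome plots by week of age, smaller windows and placebo thresholds. With an assumed gradient of 5% per year and a window of 5 years either side, the lower placebo threshold alone has 67% power, against 78% for the placebo period. Window selection on baseline balance also limits how steep a gradient can survive. Nor is a jump at exactly 65 certain to go unseen. The condition can be met by chance, under partial masking, or if the bias outweighs the benefit and the result is significant in the harmful direction.

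Three further objections have weight. The SAP states that it knows of no other intervention at 65 beyond the PRINCIPLE trial, so the jump is hypothetical. It gives no placebo-period sample size, and with few pre-CO@h patients the check would be imprecise. It also already treats nulls with caution: it warns of low power, reports confidence intervals and the power of the Neyman test, and calls a non-significant sharp result non-informative when onboarding data are missing.

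These points limit the size and severity of the concern but do not justify the condition. An imprecise check is a reason to report its interval, not to skip it. The SAP's list of explanations for an uninformative null (low uptake, threshold not followed, no effect) leaves out an opposing difference at 65, which is the one explanation item 6 could examine.

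**Conclusion.** The concern holds for a rival difference in outcomes or care located exactly at age 65. For that case item 6 is the only planned check, it is withheld after a null, and Strengths and limitations relies on it without the condition and under the wrong name. Under the stated assumptions (10,795 per group in each period, 2% control risk, relative risk 0.75, full compliance), adverse jumps of ratio 1.20 and 1.33 mean the check is skipped 81% and 95% of the time, when it would have 52% and 90% power. The jump sizes and the placebo sample size are illustrations, not estimates.

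The point does not extend to smooth age gradients, and it does not alter the primary estimate, test or population. It concerns one sensitivity analysis, so it is a should-fix: a cheap improvement that makes a null easier to interpret.

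**What to change.** In Sensitivity analyses, item 6, delete the sentence that sets the significance condition. State that the placebo period will be analysed for all three primary outcomes whatever the intention-to-treat result, in the same CCGs and with the same window as the main analysis. Report each estimate with its confidence interval and the number of patients on each side. In Strengths and limitations, refer to the placebo study period (item 6) instead of placebo outcomes, and make the wording agree with item 6.

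The difference between the CO@h-period and placebo-period estimates may be added as an exploratory figure. It assumes that everything else at 65 was stable between the periods, which Study design puts in doubt by describing a continuously changing environment, so that assumption should be stated beside it.

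The cost is one deleted sentence, one corrected reference and a little more analysis on data already planned. The drawback is that the placebo estimate may be imprecise if few pre-CO@h patients are available, and the reported interval would show this.
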